#### **8.10. Occupational Exposure**

An occupational exposure occurs when, during the performance of job duties, a person (whether a healthcare professional or otherwise) gets in unplanned direct contact with the product, which may or may not lead to the occurrence of an AE.

An occupational exposure is reported to the drug safety unit within 24 hours of the investigator's awareness, using the SAE report form, regardless of whether there is an associated AE/SAE. Since the information does not pertain to a subject enrolled in the study, the information is not reported on a CRF; however, a copy of the completed SAE report form is maintained in the investigator site file.

#### **8.11. Withdrawal Due to Adverse Events (See Also Section on [Subject Withdrawal](#))**

Withdrawal due to adverse event should be distinguished from withdrawal due to insufficient response, according to the definition of adverse event noted earlier, and recorded on the appropriate adverse event CRF page.

When a subject withdraws due to a serious adverse event, the serious adverse event must be reported in accordance with the reporting requirements defined below.

#### **8.12. Eliciting Adverse Event Information**

The investigator is to report all directly observed adverse events and all adverse events spontaneously reported by the study subject/parent(s)/legal guardian/legally acceptable representative. In addition, each study subject/parent(s)/legal guardian/legally acceptable representative will be questioned about adverse events.

#### **8.13. Reporting Requirements**

Each adverse event is to be assessed to determine if it meets the criteria for serious adverse events. If a serious adverse event occurs, expedited reporting will follow local and international regulations, as appropriate.

##### **8.13.1. Serious Adverse Event Reporting Requirements**

If a serious adverse event occurs, Pfizer is to be notified within 24 hours of investigator awareness of the event. In particular, if the serious adverse event is fatal or life-threatening, notification to Pfizer must be made immediately, irrespective of the extent of available adverse event information. This timeframe also applies to additional new information (follow-up) on previously forwarded serious adverse event reports as well as to the initial and follow-up reporting of exposure during pregnancy, exposure via breastfeeding, and occupational exposure cases.

In the rare event that the investigator does not become aware of the occurrence of a serious adverse event immediately (eg, if an outpatient study subject initially seeks treatment elsewhere), the investigator is to report the event within 24 hours after learning of it and document the time of his/her first awareness of the adverse event.

For all serious adverse events, the investigator is obligated to pursue and provide information to Pfizer in accordance with the timeframes for reporting specified above. In addition, an investigator may be requested by Pfizer to obtain specific additional follow-up information in an expedited fashion. The information collected for serious adverse events is more detailed than that captured on the adverse event case report form. In general, this will include a description of the adverse event in sufficient detail to allow for a complete medical assessment of the case and independent determination of possible causality. Information on other possible causes of the event, such as concomitant medications, vaccines, and/or illnesses must be provided. In the case of a subject death, a summary of available autopsy findings must be submitted as soon as possible to Pfizer or its designated representative.

### **8.13.2. Non-Serious Adverse Event Reporting Requirements**

All adverse events will be reported on the adverse event page(s) of the CRF. It should be noted that the form for collection of serious adverse event information is not the same as the adverse event CRF. Where the same data are collected, the forms must be completed in a consistent manner. For example, the same adverse event term should be used on both forms. Adverse events should be reported using concise medical terminology on the CRFs as well as on the form for collection of serious adverse event information.

### **8.13.3. Sponsor's Reporting Requirements to Regulatory Authorities**

Adverse events reporting, including suspected unexpected serious adverse reactions, will be carried out in accordance with applicable local regulations.

## **9. DATA ANALYSIS/STATISTICAL METHODS**

Detailed methodology for summary and statistical analyses of the data collected in this trial will be documented in a Statistical Analysis Plan, which will be dated and maintained by the sponsor. This document may modify the plans outlined in the protocol; however, any major modifications of the primary endpoint definition and/or its analysis will also be reflected in a protocol amendment.

### **9.1. Analysis of Primary Endpoint**

The primary analysis will be the evaluation of adverse events throughout the trial, laboratory tests, and physical examination.

The set of subjects for this evaluation will be the Safety population, defined as all subjects with at least 1 dose of study medication.

The following parameters will be summarized: rates of discontinuation, adverse events, ECG findings (if applicable), and laboratory abnormalities.

The Sponsor has standard algorithms for reporting adverse events and clinical laboratory test results, and these will be employed in the analysis of the data from this trial. Safety data will be subject to clinical review and summarized by appropriate descriptive statistics. Descriptive statistics for categorical data will include frequencies and/or percentages.

## 9.2. Analysis of Secondary Endpoints

The efficacy analysis will be an assessment of global response at EOIVT, EOT, 2 week and 6 week FU visits. Global response will be derived from the investigator's assessment of clinical and microbiological response as defined in [Section 7.4](#). The analysis will be conducted by frequencies and percentages of global response by determination (success, failure). These efficacy analyses will be assessed in the Modified Intent-to-Treat (MITT) population, which will be defined as all subjects who have received at least one dose of study drug and who have microbiological confirmation of *Candida* infection.

Rates of relapse (recurrence) and new infection at FU visits will also be derived from the investigator's assessment of clinical and microbiologic response as defined in [Section 7.4](#), and analyzed. Time to death will be analyzed and all-cause mortality rates determined.

## 9.3. Pharmacokinetic Analyses

### 9.3.1. Non-compartmental Pharmacokinetic Analysis

Non-compartmental pharmacokinetic analysis will be performed on individual plasma anidulafungin concentration-time data from children <2 years to obtain the following pharmacokinetic parameters of anidulafungin:  $AUC_{24}$  and  $C_{max}$ . Data listings and summary statistics will be generated for each pharmacokinetic parameter and presented in graphical and/or tabular format.

### 9.3.2. Population Pharmacokinetic-Pharmacodynamic (PK-PD) Analysis

Measures of efficacy or safety versus steady-state anidulafungin exposure ( $AUC_{24}$ ) will be modeled using a nonlinear mixed effects approach as appropriate.

Firstly, population pharmacokinetic analysis on the plasma concentration data of anidulafungin will be performed to derive the conditional estimation of individual  $AUC_{24}$ .

Population PK-PD models will be developed using an iterative process, adapting the model to improve the goodness of fit. In the case that only one record on the PD data (efficacy or safety endpoints) will be obtained from each subject, a Naïve Pooled Data (NPD) analysis will be considered for PK-PD analysis. In the case that multiple measurements are available, the time to event analysis may be explored as appropriate.

If a sufficient number of MIC values are available, the association between the PK-PD index,  $AUC/MIC$ , and efficacy will also be evaluated using the same approach. If data permit, the association between  $C_{max}/MIC$  and efficacy will be explored.

Polysorbate 80 exposure parameters (eg,  $AUC_{24}$ ,  $C_{max}$ ) will also be estimated using a nonlinear mixed effects approach as appropriate.

#### **9.4. Sample Size Determination**

Since this is a descriptive study, sample size calculations were not performed. A sample size of 60 evaluable subjects for this study was chosen based on the number of subjects estimated to be necessary to provide adequate information for assessing efficacy, safety and tolerability in children with ICC. Evaluable subjects are those that have received at least one dose of study medication and have a confirmed *Candida* infection.

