## 3. STUDY DESIGN

This prospective, open-label, non-comparative study will assess the pharmacokinetics, safety and efficacy of anidulafungin when used to treat children between the ages of 1 month and <18 years with invasive candidiasis, including candidemia (ICC).

To participate in this study, at the time of enrolment subjects must have either a confirmed diagnosis of ICC (based on the growth of *Candida* sp. from a culture obtained from a normally sterile site within 96 hours prior to enrollment), or mycological evidence highly suggestive of *Candida* sp. (eg, the growth of yeast in culture and/or the direct microscopic visualization of yeast, hyphae or pseudohyphae from a sample obtained from a normally sterile site within 96 hours prior to enrolment). Subjects may enroll and initiate study treatment prior to culture confirmation of *Candida* sp. If culture confirmation is not obtained, subjects may remain in the study and receive study treatment at the discretion of the investigator. Should the investigator choose to withdraw the subject from study treatment, the subject will discontinue study treatment but will remain in the study for continued safety monitoring for up to 6 weeks after the last dose of study treatment.

In order to accelerate the availability of PK and safety data in the lowest age group (1 month to < 2 years), the study population is broadened only in this age group to include children at risk for invasive candidiasis. Thus, eligibility criteria have been modified in Amendment 9 to additionally allow enrollment of infants (aged 1 month - < 2 years) who do not have

microbiologically confirmed *Candida* but who are at high risk of candidiasis, and for whom the investigator considers antifungal therapy with at least 5 days of IV anidulafungin to be appropriate.

All subjects meeting screening criteria will receive IV anidulafungin. Enrollment will be stratified by age (1 month - <2 years, 2 - <5 years, and 5 - <18 years), allowing  $20 \pm 2$  in each stratum.

Subjects with microbiologically confirmed ICC may be switched to oral fluconazole (6-12 mg/kg/day, maximum 800 mg/day) after at least 10 days of IV anidulafungin treatment, provided that all of the following criteria are met:

- The subject is afebrile for at least 24 hours;
- The subject is able to tolerate oral medication;
- Documentation of two blood cultures negative for *Candida* spp separated by at least 24 hours;

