In the event the investigator chooses to administer anidulafungin in combination with a second antifungal agent, anidulafungin will be discontinued following the obtainment of required blood samples for pharmacokinetic analysis as specified by the protocol; the data from these subjects will not be utilized for secondary efficacy endpoint analyses but will be assessed for safety. After the dosing regimen is confirmed by the Sponsor, enrollment will be opened to additional subjects within this age group at all investigator sites. Subsequent to this time point, the use of a second systemic antifungal agent (eg, amphotericin B) will not be permitted in any subject.

[figure not shown]
A population PK-PD analysis will also be performed in all other subjects enrolled and will include subjects <2 years of age who are not part of the 6 subject cohort described above, in which 3 to 5 sparse pharmacokinetic samples will be collected. Additionally, at the request of PDCO, pharmacokinetics of polysorbate 80, a solubilizing agent contained in the IV formulation of anidulafungin, will also be explored.

Efficacy will be based on a determination of global response (combination of clinical and microbiological response) of success or failure at the EOIVT, EOT, 2-week FU and 6-week FU visits. Rates of relapse (recurrence) and/or new infection will be assessed at the FU visits. Safety will be evaluated through assessment of adverse events and monitoring of clinical laboratory tests (hematology and serum chemistry), temperature, and physical examination results. All subjects will be followed for safety through the 6-week FU visit.

The planned enrolment is approximately 60 evaluable subjects (those subjects who have received at least one dose and confirmed *Candida* infection).

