##### 4.1. Inclusion Criteria

Subject eligibility should be reviewed and documented by an appropriate qualified member of the investigator's study team before subjects are included in the study.

Subjects must meet all of the following inclusion criteria to be eligible for enrollment into the study:

1. Subject must be either (1) at high risk for candidiasis or (2) have a definitive diagnosis of invasive candidiasis/candidemia (ICC), as defined below:
  - a. **At high risk for candidiasis (subjects 1 month to < 2 years of age only):**  
Subject is at high risk for candidiasis and antifungal therapy with anidulafungin for a minimum of 5 days is considered appropriate by the investigator.

--OR--

- b. **Definitive diagnosis of invasive candidiasis/candidemia (ICC) (all age groups)**  
is based on the growth of *Candida* sp. from a blood and/or tissue culture obtained from a normally sterile site.

For the purpose of study entry, a subject enrolled with definitive diagnosis of ICC must have at least one microbiologic AND at least one clinical criterion listed below.

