#### **9.6. Interim Analysis**

Subjects will be stratified by age (1 month - <2 years, 2 - <5 years, and 5 - <18 years), allowing  $20 \pm 2$  subjects in each stratum. An interim analysis to assess safety, PK and efficacy will be conducted when approximately  $20 \pm 2$  subjects for age cohorts 2 to <5 years and 5 to < 18 years have completed the study.

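### Does a target of 60 evaluable subjects conflict with 20 ± 2 per age stratum, now that infants without confirmed Candida can enrol?

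*Protocol*

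**What the plan says.** Protocol 9.4 reports that no sample size calculation was done because the study is descriptive. It then says "A sample size of 60 evaluable subjects for this study was chosen based on the number of subjects estimated to be necessary" for adequate information on efficacy, safety and tolerability, and adds: "Evaluable subjects are those that have received at least one dose of study medication and have a confirmed" Candida infection. The MITT efficacy set (Protocol 9.2, SAP 5.1) rests on the same two conditions.

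Protocol 3 gives the total as "The planned enrolment is approximately 60 evaluable subjects (those subjects who have received at least one dose and confirmed" Candida infection. SAP 2.1.2 also says approximately 60 evaluable.

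The stratum size appears separately. Protocol 3 has: "Enrollment will be stratified by age (1 month - <2 years, 2 - <5 years, and 5 - <18 years), allowing" 20 ± 2 in each. Protocol 9.6 and SAP 3.1 repeat 20 ± 2. They time the interim analysis by roughly that number of "subjects for age cohorts 2 to <5 years and 5 to < 18 years have completed the study". None of the three sections attaches the word evaluable to 20 ± 2.

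Two provisions allow dosed subjects who are not evaluable. Inclusion criterion 1a, for infants aged 1 month to under 2 years only, is met when "Subject is at high risk for candidiasis and antifungal therapy with anidulafungin for a minimum of 5 days is considered appropriate by the investigator". For subjects treated on suggestive mycology, Protocol 3 says: "If culture confirmation is not obtained, subjects may remain in the study and receive study treatment at the discretion of the investigator".

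**The concern.** The figure of 60 in Protocol 9.4 has the same wording as in Amendment 3 (Appendix 3), when entry at every age required confirmed or strongly suggestive mycology. Amendment 9 then opened the youngest stratum to infants with no mycological evidence, and no section says how many of them may enrol or whether they use up places in the stratum. The SAP was revised for Amendments 8 and 9 and kept approximately 60 evaluable.

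Read literally, Protocol 3 attaches 20 ± 2 to enrolment. If those places include unconfirmed infants, the efficacy set could fall well short of the number that 9.4 calls necessary. The loss would be concentrated in infants, for whom the SAP reports global response as a separate age category. That would mean a stated sample size the enrolment plan cannot deliver.

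**Working it through.** **Inputs.** Target 60 evaluable (Protocol 9.4; approximately 60 in Protocol 3 and SAP 2.1.2). Three strata of 20 ± 2 (Protocol 3 and 9.6, SAP 3.1). Exact Clopper-Pearson 95% intervals (SAP 8.1.1). Assumed success rate of 75%, close to the adult 75.6% in Protocol 1.3.2; it is not a planning value of this study. The documents give no expected share of confirmed infants, so a range is shown.

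**The plan's own figure.** There is no formula to reproduce. The only check is the sum of the strata: 3 × 18 = 54, 3 × 20 = 60, 3 × 22 = 66. The midpoint is the target, and the tolerance is 60 ± 10%, which approximately 60 covers.

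**Reading A: 20 ± 2 counts enrolled subjects.** If every older child is confirmed, evaluable N = 60 − (unconfirmed infants) at 20 per stratum:

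| Unconfirmed infants of 20 | 0 | 5 | 10 | 15 | 20 |
|---|---|---|---|---|---|
| Evaluable N | 60 | 55 | 50 | 45 | 40 |

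With no infant confirmed, N is 2 × 18 = 36, 2 × 20 = 40 or 2 × 22 = 44. Reaching 60 at 22 per stratum needs 60 − 44 = 16 of 22 infants confirmed. Unconfirmed older children would lower these figures further. Unconfirmed infants are bounded here, because the stratum holds at most 22.

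**Reading B: 20 ± 2 counts evaluable subjects.** Then 3 × 20 = 60 is met by construction and unconfirmed subjects are additional. If a share c of infants is confirmed, infants enrolled = 20/c, rounded up: 20, 27, 40 or 80 for c = 100%, 75%, 50% or 25%. Total treated is 40 more: 60, 67, 80 or 120.

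A shortfall arises only under A, and an open-ended number of unconfirmed infants only under B. The two problems cannot occur together.

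**Which reading the text supports.** Protocol 3 uses enrolment for the strata but also states planned enrolment as approximately 60 evaluable subjects. Three strata of 20 give exactly that. Reading B therefore fits the section as a whole, although no sentence settles it.

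**What Reading A would cost.** Lower limit = Beta quantile 0.025 with parameters (x, n − x + 1); upper limit = Beta quantile 0.975 with parameters (x + 1, n − x).

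| Set | x/n | 95% CI (%) | Half-width (points) |
|---|---|---|---|
| Pooled | 45/60 | 62.1–85.3 | 11.6 |
| Pooled | 30/40 | 58.8–87.3 | 14.3 |
| Pooled | 27/36 | 57.8–87.9 | 15.0 |
| Infants | 15/20 | 50.9–91.3 | 20.2 |
| Infants | 12/16 | 47.6–92.7 | 22.6 |
| Infants | 6/8 | 34.9–96.8 | 31.0 |

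The infant estimate is imprecise even with all 20 confirmed. The protocol sets no target precision that any of these rows would miss.

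**Primary analysis.** Safety uses all dosed subjects (Protocol 9.1), so that set holds 54 to 66 under A and at least 54 under B. For an event with an assumed true rate of 5%, the chance of seeing at least one is 1 − 0.95^54 = 93.7% and 1 − 0.95^60 = 95.4%.

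**PK sub-study infants.** For those given a second antifungal, Protocol 3 says "the data from these subjects will not be utilized for secondary efficacy endpoint analyses but will be assessed for safety". If confirmed, they still meet the 9.4 definition of evaluable, so they do not reduce the count of 60. Their absence from the efficacy tables is stated openly and predates Amendment 9 (Appendix 4).

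**The case for a change.** The strongest case for a change is that both readings leave something unsaid. Under A, the word approximately can absorb 54 to 66 but not 36 to 44, and 9.4 omits that word. Under B, the total number of children treated is undefined and sites are not told when the infant stratum is full. Amendment 9 was written to speed up PK and safety data in infants, so unconfirmed infants are expected. Protocol 9.4 also ties its 60 to children with ICC: with only 40 confirmed, the chance of seeing a 5% event among them is 1 − 0.95^40 = 87.1%, against 95.4% at 60. One sentence would settle the unit at almost no cost.

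It stands that the unit is not stated and that a sentence would help a reader anticipate the efficacy number. It does not stand that the plan contradicts itself. The low figures need two conditions together: the enrolled reading, which Protocol 3 does not force, and no confirmed infants at all, although criterion 1b still admits them. Amendment 9's stated purpose also explains why at-risk infants were never meant to supply efficacy data: response is assessed only in confirmed subjects (Schedule of Activities, footnote 23).

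**Conclusion.** No change to the plan follows. This is missing detail about a counting unit, and it is handled without harm. No hypothesis is tested (SAP 4.1), no power or error rate depends on 60, and the primary safety analysis takes every dosed subject under either reading. Membership of the MITT set is fixed by dosing and confirmation, so analysts need no decision about 20 ± 2 to build it. SAP 8.2.2 reports the number of observations with each rate, and the exact intervals widen by themselves if fewer infants are confirmed.

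The size of the issue is nil under the evaluable reading. Under the enrolled reading at 20 per stratum, the worst case is an efficacy set of 40 instead of 60, which adds 14.3 − 11.6 = 2.7 points to the pooled half-width, with wider intervals in infants. These figures assume 75% success and that all older children are confirmed; the confirmed share in infants is not in the documents. A clarifying sentence at the next routine revision would be reasonable housekeeping, but it would alter no analysis and no conclusion.

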#### **9.5. Safety Analysis**

All subjects who have received at least 1 dose of study medication will be included in the safety analyses. Adverse events and other safety data, including ECG (if applicable) and laboratory data will be reviewed and summarized on an ongoing basis during the study. The Sponsor has standard algorithms for reporting adverse events and clinical laboratory test results, and these will be employed in the analysis of the data from this study. Safety and tolerability data will be presented in tabular and/or graphical format and summarized descriptively, where appropriate.

#### **9.6. Interim Analysis**

Subjects will be stratified by age (1 month - <2 years, 2 - <5 years, and 5 - <18 years), allowing  $20 \pm 2$  subjects in each stratum. An interim analysis to assess safety, PK and efficacy will be conducted when approximately  $20 \pm 2$  subjects for age cohorts 2 to <5 years and 5 to < 18 years have completed the study.

#### **9.7. Data Monitoring Committee**

This study will use an Independent Data Monitoring Committee (IDMC).

The IDMC will be responsible for ongoing monitoring of the efficacy and safety of subjects in the study according to the Charter. Any recommendations made by the IDMC to alter the conduct of the study will be forwarded to Pfizer for final decision. Pfizer will forward such decisions, which may include summaries of aggregate analyses of endpoint events and of safety data which are not endpoints, to regulatory authorities, as appropriate. In this instance, such disease-related efficacy endpoints are not reported individually as SAEs.

